7.5.4 Adverse Events Leading to Discontinuation of Study Therapy

Summary:

Adverse Events leading to discontinuation will be summarized by treatment:

- Overall summary of AEs leading to discontinuation by worst CTC grade (grade 1, 2, 3, 4, 5, unknown) presented by SOC/PT
- Overall summary of AEs leading to discontinuation by worst CTC grade (any grade, grade 3-4, grade 5) presented by SOC/PT.
- Overall summary of drug-related AEs leading to discontinuation by worst CTC grade (grade 1, 2, 3, 4, 5, unknown) presented by SOC/PT
- Overall summary of drug-related AEs leading to discontinuation by worst CTC grade (any grade, grade 3-4, grade 5) presented by SOC/PT.

Listing:

- All AEs leading to discontinuation for All Treated Subjects.

7.5.5 Adverse Events Leading to Dose Modification

Summary:

AEs leading to dose delay/interruption/reduction will be summarized for each treatment:

- Overall summary of AEs leading to dose delay/ interruption/reduction by worst CTC grade (grade 1, 2, 3, 4, 5, unknown) presented by SOC/PT
- Overall summary of drug-related AEs leading to dose delay/interruption/reduction by worst CTC grade (grade 1, 2, 3, 4, 5, unknown) presented by SOC/PT

Listing:

By-subject AEs leading to dose delay/interruption/reduction listing will be provided.

- All AEs leading to dose delay/interruption/reduction for All Treated Subjects.

7.5.6 Multiple Events

Analyses that take into account the multiple occurrences of a given adverse event will be conducted. To prepare these analyses, the CRF data will be processed according to standard BMS algorithms⁵ in order to collapse adverse event records into unique records based on the preferred term. This data will be presented as the rate per 100 person-years of exposure. These analyses will take into account all on-treatment events (allowing more than 1 event per subject) and the total exposure time. The person-year exposure will be computed as the sum over the subjects' exposure expressed in years where the exposure time is defined as

- Date of last dose of study treatment - date of first dose of study treatment + 61 days (+ 101 days for Part 3 and 4), for subject who are off study treatment and were followed for at least 60 days (100 days for Part 3 and 4) after last dose of study treatment.
- Last known date alive- date of first dose of study treatment + 1, for subjects who are still on-treatment or who are off study treatment and were followed less than 60 days (or 100 days for Part 3 and 4) after last dose of study treatment.

When specified the 95%CI of the rate per 100 person-year of exposure will be derived using normal approximation and variance estimation proposed in Cook and Lawless⁶ (optional).

Summary:

The following summary tables will be provided for each treatment:

- Total number and rate (exposure adjusted) of occurrences for all AEs occurring in at least 5% of the subjects treated per study treatment.

Listing:

- Listing displaying the unique instances of all AEs, i.e., after duplicates have been eliminated and overlapping and contiguous occurrences of the same event (i.e. same PT) have been collapsed will be provided.

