6.1.1 Serious Adverse Event Collection and Reporting

Sections 5.6.1 and 5.6.2 in the IB¹⁴ represent the Reference Safety Information to determine expectedness of SAEs for expedited reporting. Following the subject's written consent to participate in the study, all SAEs, whether related or not related to study drug, must be collected, including those thought to be associated with protocol-specified procedures. All SAEs must be collected that occur during the screening period and within a total of 60 days of discontinuation of dosing for BMS-986183 dose escalation (Part 1) and BMS-986183 dose expansion (Part 2) and within a total of 100 days of discontinuation of dosing for BMS-986183 and nivolumab dose escalation (Part 3) and BMS-986183 and nivolumab dose expansion (Part 4). If applicable, SAEs must be collected that relate to any later protocol-specified procedure (eg, a follow-up skin biopsy).

The investigator must report any SAE that occurs after these time periods and that is believed to be related to study drug or protocol-specified procedure.

An SAE report must be completed for any event where doubt exists regarding its seriousness.

If the investigator believes that an SAE is not related to study drug, but is potentially related to the conditions of the study (such as withdrawal of previous therapy or a complication of a study procedure), the relationship must be specified in the narrative section of the SAE Report Form.

SAEs, whether related or not related to study drug, and pregnancies must be reported to BMS or designee within 24 hours of awareness of the event. SAEs must be recorded on the SAE Report Form; pregnancies on a Pregnancy Surveillance Form (electronic or paper forms). The preferred method for SAE data reporting collection is through the eCRF. The paper SAE/pregnancy surveillance forms are only intended as a back-up option when the eCRF system is not functioning. In this case, the paper forms are to be transmitted via email or confirmed facsimile (fax) transmission to:

SAE Email Address: Refer to Contact Information list.

SAE Facsimile Number: Refer to Contact Information list.

For studies capturing SAEs through electronic data capture, electronic submission is the required method for reporting. In the event the electronic system is unavailable for transmission, paper forms must be used and submitted immediately. When paper forms are used, the original paper forms are to remain on site.

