6.1.2 Post-baseline period

- On-treatment AEs will be defined as AEs with an onset date and time on or after the date and time of the first dose of study treatment (or with an onset date on or after the day of first dose of study treatment if time is not collected or is missing). For subjects who are off study treatment, AEs will be included in summaries if event occurred within a safety window of 60 days after the last dose of study for BMS-986183 monotherapy dose escalation period (Part 1) and BMS-986183 monotherapy dose expansion period (Part 2) and of 100 days after the last dose of study drug for BMS-986183 and nivolumab combination therapy dose escalation (Part 3) and BMS-986183 and nivolumab combination therapy dose expansion (Part 4).
- On-treatment evaluations (laboratory tests, pulse oximetry and vital signs) will be defined as evaluations taken after the day (and time, if collected and not missing) of first dose of study treatment. For subjects who are off study treatment, summaries will include measurements

within a safety window of 60 days after the last dose of study for BMS-986183 monotherapy dose escalation period (Part 1) and BMS-986183 monotherapy dose expansion period (Part 2) and of 100 days after the last dose of study drug for BMS-986183 and nivolumab combination therapy dose escalation (Part 3) and BMS-986183 and nivolumab combination therapy dose expansion (Part 4).

- Tumor assessments will be slotted in the post-baseline period if assessments are after start of the treatment date.

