For retreated subject in Part 3 and 4, the initial off-treatment period is included in all safety analysis as if the retreated subject were still on treatment in that period of time.

For the analyses (during original assigned treatments) of subjects treated with the combination therapy extension option in Part 2, all the safety assessment will be truncated at the first dose date of the combination therapy. All others will follow regular counting rules. For the analysis of subjects treated with the combination therapy extension option during the combination period, all the safety assessments will be counted from the first dose of combination therapy and up to 100 days after last dose (optional analyses).

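### Person-time for Part 2 crossovers is not stopped at the first combination dose, where AE counting stops, so exposure-adjusted Part 2 monotherapy AE rates are understated

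*SAP*

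**What the plan says.** **The rate (SAP 7.5.6).** Recurrent adverse events are reported per 100 person-years: "These analyses will take into account all on-treatment events (allowing more than 1 event per subject) and the total exposure time". Person-time is summed over subjects by one of two rules.

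- Off treatment with full follow-up: "Date of last dose of study treatment - date of first dose of study treatment + 61 days", with a longer tail of "101 days for Part 3 and 4".
- Otherwise: "Last known date alive- date of first dose of study treatment + 1, for subjects who are still on-treatment", and likewise for subjects off treatment who were followed for less than the full window.

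Neither rule mentions Part 2 subjects who cross over to the combination.

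**The event window.** For Parts 1 and 2, SAP 6.1.2 says "AEs will be included in summaries if event occurred within a safety window of 60 days after the last dose of study". SAP 7.5 makes an exception for Part 2 subjects who take the combination extension. In the analysis of their originally assigned treatment, "all the safety assessment will be truncated at the first dose date of the combination therapy". An optional second analysis counts their events from the first combination dose to 100 days after the last dose.

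**Timing of the crossover (Protocol 3.1.2.1).** The first combination dose comes at least 21 days and at most 6 weeks after the last BMS-986183 monotherapy dose. The extension may run for up to 17 cycles of 21 days.

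**The concern.** An event rate is interpretable only if the events and the person-time come from the same interval. For Part 2 crossovers the SAP closes the numerator at the first combination dose and leaves the denominator open. The extra days carry no countable events, so they pull the monotherapy rate down.

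Two things are at stake. First, the extension is offered in Part 2 and not in Part 1, so monotherapy rates from the two parts would not be comparable even at the same dose. Second, 7.5.6 does not say whether combination doses count as study treatment in this formula. Two programmers could produce different tables, and neither table would be correct.

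**Working it through.** **Notation (days)**

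- D: first to last monotherapy dose.
- G: last monotherapy dose to first combination dose, 21 to 42 (Protocol 3.1.2.1).
- C: first to last combination dose, 0 to 16 × 21 = 336 (17 cycles at most).

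**Step 1. The SAP's own figures.** From the first dose through 60 days after the last dose, counted inclusively, is D + 60 + 1 = D + 61 days. With a 100-day window it is D + 101. Both tails in 7.5.6 are reproduced, and for a subject who does not cross over they match the event window exactly.

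**Step 2. A Part 2 crossover, original-treatment analysis.**

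- Event window, first monotherapy dose to the day before the first combination dose: D + G.
- Person-time, reading A (study treatment means monotherapy doses only): D + 61.
- Person-time, reading B (combination doses also count): D + G + C + 61.

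Excess under A is 61 − G, which is 61 − 42 = 19 to 61 − 21 = 40 days. Excess under B is C + 61, which is 61 to 336 + 61 = 397 days. Since G cannot exceed 42, the excess is positive on both readings. A crossover who falls under the second rule is followed to the last known date alive. That is also not cut at the first combination dose.

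**Step 3. One subject.** Assume 6 monotherapy cycles (D = 5 × 21 = 105), G = 28, and 4 combination cycles (C = 3 × 21 = 63). The event window is 105 + 28 = 133 days.

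| Reading | Person-time | Stated rate / matched rate | Understated by |
|---|---|---|---|
| A | 105 + 61 = 166 | 133/166 = 0.80 | 20% |
| B | 105 + 28 + 63 + 61 = 257 | 133/257 = 0.52 | 48% |

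**Step 4. The cohort rate.** Because 7.5.6 sums exposure over subjects, the reported rate is affected only in proportion to crossover. Assume 50 subjects, all with D = 84; crossovers have G = 28 and, for reading B, C = 84. A non-crossover contributes 84 + 61 = 145 days to both window and person-time. A crossover has a window of 84 + 28 = 112 days, and person-time of 145 days (A) or 84 + 28 + 84 + 61 = 257 days (B). The event count is the same either way, so the ratio of rates is the ratio of mean days per subject.

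| Crossing over | Matched days per subject | A: days, ratio | B: days, ratio |
|---|---|---|---|
| 10% | 141.7 | 145, 0.98 | 156.2, 0.91 |
| 30% | 135.1 | 145, 0.93 | 178.6, 0.76 |
| 50% | 128.5 | 145, 0.89 | 201.0, 0.64 |

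The understatement is about 2% to 11% under A and 9% to 36% under B.

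**Step 5. The optional combination-period analysis.** Its event window is C + 101. If person-time restarts at the first combination dose but keeps the Part 2 tail, it is C + 61. With C = 84 that is 185 against 145 days, and the rate is overstated by a factor of 185/145 = 1.28. The factor is 101/61 = 1.66 at C = 0 and 437/397 = 1.10 at C = 336.

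**The case against.** **Truncation may be meant to cover exposure.** SAP 7.5 truncates all safety assessment, and 7.5.6 lies within that section. A sensible programmer might stop person-time at the same date. But person-time is not an assessment, and 7.5.6 gives its own explicit definition, with a special tail for Parts 3 and 4 and nothing for crossovers. The intention may be right, but the text does not say it.

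**Reading B may be too harsh.** SAP 6.2 lists monotherapy and combination as separate as-treated regimens, and the 7.5.6 table is produced for each treatment. A monotherapy row could therefore end at the last monotherapy dose plus 61 days. This stands as a fair reading, so the size must be given on both. It does not remove the problem, because reading A still leaves 19 to 40 days too many under the +61 rule.

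**The table is secondary.** The primary endpoints in SAP 4.1 are incidences of AEs and SAEs by worst grade, AEs leading to discontinuation, deaths and laboratory grade shifts. None uses person-time. The confidence interval for the rate is optional, and Protocol 8.5 plans no formal testing. Crossover also requires that the combination dose has been found safe in Part 3, so the share could be small. All of this stands and limits the importance.

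**Retreated subjects in Parts 3 and 4.** A reader might infer the same mismatch for them, because the off-treatment gap enters person-time. The documents do not support that. SAP 7.5 says "the initial off-treatment period is included in all safety analysis as if the retreated subject were still on treatment", so the event window spans the gap too, with the same 100-day tail. For example, with 336 days in the first course, a 240-day gap and 84 days in the second, both window and person-time are 336 + 240 + 84 + 101 = 761 days.

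A separate question is how completely events are captured in that gap. Protocol 6.1.1 requires all SAEs "within a total of 100 days of discontinuation of dosing" in Parts 3 and 4, and survival telephone contacts collect only survival and subsequent therapy. Against this, related SAEs remain reportable later. Nonserious AE collection may extend to a later last scheduled visit (Protocol Table 5.1-1), and the retreatment Day 0 visit takes an interim AE and SAE history. That is a matter of ascertainment, not of mismatched windows.

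**Conclusion.** The person-time rule in SAP 7.5.6 is wrong as written for Part 2 crossovers in the original-treatment analysis, and it understates the monotherapy AE rates. The direction there does not depend on which doses count as study treatment; only the size does.

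The single-subject figures of 20% and 48% should not be read as the error in the reported rate. That error depends on the crossover share and on treatment durations, which the documents do not give. The cohort ranges rest on the assumptions in step 4 and are illustrative.

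A reader might also infer that the error always lowers a rate. It does not: it is nil for retreated subjects, and in the optional combination-period analysis an unchanged 61-day tail would raise the rate. The primary safety endpoints are not affected.

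**What to change.** Add to SAP 7.5.6:

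- For Part 2 subjects who take the combination extension, person-time in the original-treatment analysis ends at the first combination dose under both person-time rules. Use the same day boundary as for events.
- In the optional combination-period analysis, person-time starts at the first combination dose and uses the +101-day tail, to match the 100-day event window in SAP 7.5.

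With the first change, person-time for a crossover equals D + G and the rate ratio is 1. No change is needed for retreated subjects. The cost is two sentences in the SAP and a small programming change, with no effect on data collection.

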7.5.7 Adverse Events of Special Interest

The Adverse Events of Special Interest (AEOSIs) consist of a list of preferred terms grouped by specific category which have been identified of interest for BMS-986183. Nivolumab AEOSI (also referred to as ‘Select AE’) consist of a list of preferred terms grouped by specific category (e.g., pulmonary events, gastrointestinal events categories). These AEs and the categories are defined by the Sponsor and the list that is the most current at the time of analysis will be used.

AEOSI for BMS-986183 and Nivo will be analyzed separately, if there is any identified as the program matures and more safety data is collected.

Summary:

AEOSIs will be summarized by treatment for each category:

- Overall summary of any AEs by worst CTC grade presented by Category/PT (any grade, grade 3-4, grade 5)
- Overall summary of drug-related AEs by worst CTC grade presented by Category/ PT (any grade, grade 3-4, grade 5)
- Overall summary of any AEs leading to discontinuation by worst CTC grade presented by Category/PT (any grade, grade 3-4, grade 5)
- Overall summary of drug-related select AEs leading to discontinuation by worst CTC grade presented by Category/PT (any grade, grade 3-4, grade 5)
- Overall summary of any AEs by worst CTC grade presented by Category/PT (grade 1, 2, 3, 4, 5, unknown)
- Overall summary of drug-related AEs by worst CTC grade presented by Category/ PT (grade 1, 2, 3, 4, 5, unknown)

Listing:

By-subject AEOSI listing will be provided by category.

7.5.8 Clinical Laboratory Evaluations

Clinical laboratory data will be analyzed using International System of Units (SI). Analyses will be repeated using US conventional units for the clinical study report. Relevant parameters will be fully toxicity graded per CTCAE v4.03.

Summary:

Laboratory parameters will be summarized by treatment as worst CTC grade on-treatment per subject and as shift table of worst on-treatment CTC grade compared to baseline CTC grade per subject.

Listing:

A by-subject listing of laboratory parameters will be provided.

7.5.8.1 Abnormal Hepatic Function Tests

Summary:

The number of subjects with the following laboratory abnormalities from on-treatment evaluations will be summarized by treatment:

- AST or ALT $> 3, 5, 10, 15, \text{ or } 20 \times \text{ULN}$
- Total bilirubin $> 2 \text{ or } 8 \times \text{ULN}$
- AST or ALT $> 10 \times \text{ULN}$ for $> 2 \text{ weeks}$
- Total bilirubin $> 8 \times \text{ULN}$ for subjects with elevated total bilirubin at study entry or $> 5 \times \text{ULN}$ for those with normal total bilirubin at entry or
- Concurrent (within 1 day)
 - ALT $\geq 10 \times \text{ULN}$ and
 - total bilirubin $\geq 2 \times \text{ULN}$ or baseline if elevated total bilirubin at entry

Figure:

The following scatterplots will be produced for the following hepatic laboratory parameters:

- Total bilirubin peak vs. AST peak
- Total bilirubin peak vs. ALT peak

On-treatment peak total bilirubin and on-treatment peak AST/ALT may or may not happen on the same day of liver testing.

Listing:

A by-subject listing of these specific abnormalities will be provided.

7.5.8.2 Abnormal Thyroid Function Test

Summary:

The number of subjects with the following laboratory abnormalities from on-treatment evaluations will be summarized by treatment group for Part 3 and 4:

- TSH value > ULN and
 - with baseline TSH value <= ULN
 - at least one FT3/FT4 test value < LLN
- TSH < LLN and
 - with baseline TSH value >= LLN
 - at least one FT3/FT4 test value > ULN

Listing:

A by-subject listing of these specific abnormalities will be provided.

7.5.9 Vital Signs and Physical Examination Abnormalities

Listing:

- Vital signs for all treated subjects
- Physical examination abnormalities for all treated subjects
- Diagnostic procedures for all treated subjects

7.5.10 Electrocardiogram

Summary:

- For heart rate (HR), QT, Δ QTcF, and PR, summary measures (n, mean, standard deviation, median, minimum, and maximum) and the corresponding changes from baseline will be provided by treatment and study date.
- Frequency distribution of maximum QTcF, maximum Δ QTcF, maximum QRS, maximum PR interval and maximum heart rate by treatment within pre-specified intervals:
 - For QTcF: QTcF \leq 450 msec, 450 msec < QTcF \leq 480 msec, 480 msec < QTcF \leq 500 msec, QTcF > 500 msec
 - For Δ QTcF: Δ QTcF \leq 30 msec, 30 msec < Δ QTcF \leq 60 msec, Δ QTcF > 60 msec
 - For PR: PR \leq 200 msec, PR > 200 msec
 - For QRS: QRS \leq 120 msec, QRS > 120 msec

Figure:

- Scatter plot and regression of Δ QTcF on active ADC, conjugated tubulysin, and unconjugated tubulysins, respectively.

Listing:

- ECG measures through EOT
- ECG abnormalities

7.5.11 Pregnancy

Listing:

- By-subject listing of pregnancy tests results will be provided for all treated female subjects.

7.6 Other analyses

Additional exposure response analysis may be performed to explore associations of exposure with biomarkers, selected safety measures, and/or efficacy measures.

8 CONVENTIONS

The following conventions may be used for imputing partial dates for analyses requiring dates: For missing and partial adverse event onset dates, imputation will be performed using the Adverse Event Domain Requirements Specification⁷. Missing and partial Non-Study Medication Domain dates will be imputed using the derivation algorithm described in 4.3.3 of BMS Non-Study Medication Domain Requirements Specification⁸.

For death dates, the following conventions will be used for imputing partial dates:

- If only the day of the month is missing, the 1st of the month will be used to replace the missing day. The imputed date will be compared to the last known date alive day and the maximum will be considered as the death date.
- If the month or the year is missing, the death date will be imputed as the last known date alive day
- If the date is completely missing but the reason for death is present the death date will be imputed as the last known date alive day

For date of progression, the following conventions will be used for imputing partial dates:

- If only the day of the month is missing, the 1st of the month will be used to replace the missing day*.
- If the day and month are missing or a date is completely missing, it will be considered as missing.

*In cases where the date of death is present and complete, the imputed progression date will be compared to the date of death. The minimum of the imputed progression date and date of death will be considered as the date of progression.

For other partial/missing dates, the following conventions may be used:

- If only the day of the month is missing, the 15th of the month will be used to replace the missing day.
- If both the day and the month are missing, “July 1” will be used to replace the missing information.
- If a date is completely missing, it will be considered as missing.

The following conversion factors will be used to convert days to months or years: 1 month = 30.4375 days and 1 year = 365.25 days.

Duration (e.g. time from first diagnosis to first dosing date, duration of response, and time to response) will be calculated as follows:

$$\text{Duration} = (\text{Last date} - \text{first date} + 1)$$

